#### **14.1 External Data Auditing**

The study data will be audited by a member of the QASMC office on annual basis as per institutional guidelines.

### **15.0 ENDPOINTS**

#### **15.1 Primary Outcome Analyses**

The primary endpoint for each arm of the phase II portion of this trial is the proportion of confirmed tumor responses. A confirmed response is defined to be a CR, VGPR, or PR noted as the objective status. Response will be evaluated using up to 12 cycles of treatment. All participants meeting the eligibility criteria who have signed a consent form and have begun treatment will be evaluable for response.

#### **15.2 Secondary Outcome Analyses**

Survival time is defined as the time from registration to death due to any cause. The distribution of survival time will be estimated using the method of Kaplan-Meier for the participants included in evaluating the decision criteria.

Progression-free survival time is defined as the time from registration to disease progression, clinical relapse, or death due to any cause. The distribution of progression-free survival will be estimated using the method of Kaplan-Meier.

Duration of overall response is defined for all participants who have achieved a confirmed response as the date at which the participant's objective status is first noted to be a CR, sCR, nCR, VGPR, or PR to the earliest date progression or clinical relapse is documented. The distribution of duration of response will be estimated using the method of Kaplan-Meier.

## **16.0 STATISTICAL ANALYSIS**

In the Phase 2 portion, the largest success proportion where the proposed treatment regimen would be considered ineffective in this population is 20%, and the smallest success proportion that would warrant further treatment is 40%. The following one-stage design uses 24 participants to test the null hypothesis that the true success proportion is at most 20%.

Enter 24 participants into the phase 2 portion of the study. If 7 or fewer successes are observed, we will consider this treatment ineffective in this participant population. If 8 or more successes are observed, we may recommend further testing of the regimen in subsequent studies in this population.

Power and Significance Level: Assuming that the number of successes is binomially distributed, the significance level is 0.10, i.e. there is a 10% chance of finding the drug to be effective when it truly is not. The probability of declaring that this regimen warrants further study (i.e. statistical power) under various success proportions, and the probability of stopping after the first stage can be tabulated as a function of the true success proportion.

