## Phase II

Seventeen participants will be treated at the MTD of carfilzomib in combination with PLD and dexamethasone to evaluate the efficacy and toxicity in participants with relapsed or refractory multiple myeloma. Participants treated in phase 1 at the MTD will be counted as part of the phase two accrual.

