## 5.3 Phase II

Having established an MTD in phase I, phase II will be conducted to assess the efficacy and toxicity of carfilzomib in combination with PLD and dexamethasone in participants with relapsed or refractory multiple myeloma.

Seventeen participants will be treated at the MTD of carfilzomib in combination with PLD and dexamethasone. Participants treated in phase 1 at the MTD will be counted as part of the phase two accrual. If  $\leq 5$  successes (CR, VGPR, or PR) are observed, we will

consider this regimen ineffective in this participant population and will not recommend further testing.

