#### **5.5 Accrual**

The anticipated accrual rate for the phase I portion is 1 participant per calendar month, with a total accrual time of two years. The anticipated accrual rate for the phase II portion is 1-2 participants per calendar month, with a total accrual time of one year.

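### Phase II has two incompatible designs: 17 participants, ineffective at 5 or fewer responses (section 5.3), and 24 participants, ineffective at 7 or fewer (section 16.0)

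*Combined protocol and SAP*

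**What the plan says.** The phase II part of the schema gives the number only: "Seventeen participants will be treated at the MTD of carfilzomib in combination with PLD and dexamethasone to evaluate the efficacy and toxicity". Section 5.3 repeats it ("Seventeen participants will be treated at the MTD of carfilzomib in combination with PLD and dexamethasone") and adds a decision rule. With 5 or fewer "successes (CR, VGPR, or PR) are observed, we will" "consider this regimen ineffective in this participant population and will not recommend further testing". Both places also say: "Participants treated in phase 1 at the MTD will be counted as part of the phase two accrual".

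Section 16.0 sets out a different design. It takes 20% as the highest response rate that would count as ineffective and 40% as the lowest that would justify further work. It continues: "The following one-stage design uses 24 participants to test the null hypothesis that the true success proportion is at most 20" per cent. The instruction is "Enter 24 participants into the phase 2 portion of the study". Seven or fewer responses means ineffective; with 8 or more, further testing may be recommended. The significance level is given as 0.10. No power figure is stated and no table of operating characteristics is supplied.

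On timing, section 5.5 says: "The anticipated accrual rate for the phase II portion is 1-2 participants per calendar month, with a total accrual time of one year".

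**The concern.** The plan gives two sample sizes and two cut-offs for one primary decision. Section 15.1 makes the proportion of confirmed responses the primary phase II endpoint, and these are the only rules for acting on it. Section 16.0 gives a statistical basis for 24 participants; section 5.3 gives none for 17.

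In a single-arm trial with no comparator, two rules in force at once mean that a choice made after responses are known could be defended from the protocol either way. For example, 6 responses in the first 17 participants passes section 5.3, and 7 responses in all 24 fails section 16.0; one series of participants can give both results. The target accrual that section 14.0 requires in each semi-annual monitoring report is also unclear.

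**Working it through.** **Inputs.** Null rate 20%, target rate 40%, significance level 0.10 and the rule of 24 participants with at least 8 responses to pass: section 16.0. Seventeen participants with at least 6 to pass (the complement of 5 or fewer): section 5.3. The null hypothesis is that the rate is at most 20%, so the test is one-sided.

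**Formula.** The probability of passing at true rate p is P(X ≥ r) = Σ C(n,k) p^k (1−p)^(n−k), summed over k = r to n. Alpha is this value at p = 0.20 and power is its value at p = 0.40.

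**The section 16.0 design.** With n = 24 and r = 8, alpha = 0.0892 and power = 0.8081. The stated 0.10 holds as a ceiling and is not the attained level. The plan states no power target. If 80% is assumed, 24 with a pass at 8 is the smallest exact design with alpha at or below 0.10. Assuming 85% gives 28 participants, and 90% gives 36.

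**Both rules, and the two mixtures a reader could form from the text:**

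| Participants | Responses to pass | Alpha at 20% | Power at 40% | False-negative rate at 40% |
|---|---|---|---|---|
| 24 (section 16.0) | 8 | 0.0892 | 0.8081 | 0.1919 |
| 17 (section 5.3) | 6 | 0.1057 | 0.7361 | 0.2639 |
| 17 | 8 | 0.0109 | 0.3595 | 0.6405 |
| 24 | 6 | 0.3441 | 0.9600 | 0.0400 |

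The power difference between the two stated rules is 0.8081 − 0.7361 = 0.0720. The lowest passing response rates are 8/24 = 33.3% and 6/17 = 35.3%. To keep alpha at or below 0.10 with 17 participants, 7 responses are needed; alpha is then 0.0377 and power 0.5522.

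**How often the rules disagree.** Apply the section 5.3 rule to the first 17 participants and the section 16.0 rule to all 24, with independent responses at a common rate. The probability of opposite decisions is 0.073 at a true rate of 20%, 0.169 at 30% and 0.141 at 40%.

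**Can the two texts be reconciled?**
- *Seventeen new participants plus phase I carry-over.* The carry-over sentence directly follows the seventeen and counts phase I participants at the MTD in the phase II accrual, so its natural meaning puts them inside that number. If they were extra, a 3 + 3 dose level holds up to 6 participants evaluable for the MTD, and 17 + 6 = 23. The cut-offs would still be 5 in one place and 7 in the other.
- *Seventeen treated, 24 entered.* Section 15.1 counts every eligible, consented participant who has begun treatment. Nothing in the plan describes seven who are entered and not treated.
- *Seventeen as a first stage, 24 as the total.* Section 16.0 calls the design one-stage. It does later mention the chance of stopping after a first stage, but no such stage is defined.
- *Accrual.* One to two participants a month for 12 months gives 12 to 24, which admits both numbers.

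**The case against.** The strongest reply is that section 16.0 is a complete and reproducible design, while section 5.3 carries a rule with no stated basis, so a reader could treat the statistics section as governing. The practical gap is also modest: alpha of 0.106 against 0.10 is a small excess, the lowest passing rates differ by only 2 percentage points, and lower power contradicts nothing because no power target is stated. The carry-over arithmetic is not conclusive either. Section 6.1 allows participants who are not evaluable for the MTD to stay on treatment and be replaced, so more than six could be treated at one dose level.

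Much of this is fair. The lower power at 17 is a cost to disclose and not an error in itself. The figure of 23 should not be pressed, and accrual is no evidence for either version. The rule is also firm only on the negative side, since section 16.0 merely permits a recommendation at 8 or more. None of this removes the conflict. No text gives section 16.0 precedence, the number 17 appears in two places, and the cut-offs differ however the carry-over sentence is read.

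**Conclusion.** The concern holds and must be fixed. The plan does not settle how many participants to treat in phase II or how many responses are needed, and the error rates depend on which section is followed. Under the section 16.0 hypotheses, the section 5.3 rule has alpha 0.106, just above the stated 0.10. It would discard a regimen with a true 40% response rate 26.4% of the time, against 19.2% for the section 16.0 rule.

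These figures assume independent binomial responses and the 20% and 40% rates, which the plan states only alongside 24 participants. The documents do not show which version the sponsor intends.

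**What to change.** State one sample size and one cut-off, identically in the schema, section 5.3 and section 16.0, with the exact operating characteristics.

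- **If 17 is intended:** rewrite section 16.0 for 17 participants, ineffective at 5 or fewer, with exact one-sided alpha 0.106 and power 0.736 at 40%. Remove the 0.10 statement and acknowledge the 26.4% false-negative rate. This costs only a wording amendment. If 0.10 has to stay as a ceiling with 17 participants, the pass mark becomes 7 responses and power falls to 0.552.
- **If 24 is intended:** change the schema and section 5.3 to 24 participants, ineffective at 7 or fewer, with exact alpha 0.089 and power 0.808. This needs 24 − 17 = 7 more participants, or 7/2 = 3.5 to 7/1 = 7 more months at the stated rate. Without carry-over, the one-year accrual in section 5.5 then holds only at 2 a month. If six phase I participants carry over, it needs (24 − 6)/12 = 1.5 a month.

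Two small edits belong in the same amendment. Delete the first-stage stopping remark from section 16.0. Say explicitly that the carried-over phase I participants are those treated in Part 2 at the three-drug MTD and that they count within the chosen total.

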## APPENDIX A: ECOG Performance Status Scale

Grade	Description
0	Normal activity. Fully active, able to carry on all pre-disease performance without restriction.
1	Symptoms, but ambulatory. Restricted in physically strenuous activity, but ambulatory and able to carry out work of a light or sedentary nature (e.g., light housework, office work).
2	In bed <50% of the time. Ambulatory and capable of all self-care, but unable to carry out any work activities. Up and about more than 50% of waking hours.
3	In bed >50% of the time. Capable of only limited self-care, confined to bed or chair more than 50% of waking hours.
4	100% bedridden. Completely disabled. Cannot carry on any self-care. Totally confined to bed or chair.
5	Dead.

## APPENDIX B: Karnofsky Performance Status Scale

DEFINITIONS	RATING (%)	CRITERIA
Able to carry on normal activity and to work; no special care needed.	100	Normal no complaints; no evidence of disease.
	90	Able to carry on normal activity; minor signs or symptoms of disease.
	80	Normal activity with effort; some signs or symptoms of disease.
Unable to work; able to live at home and care for most personal needs; varying amount of assistance needed.	70	Cares for self; unable to carry on normal activity or to do active work.
	60	Requires occasional assistance, but is able to care for most of his personal needs.
	50	Requires considerable assistance and frequent medical care.
Unable to care for self; requires equivalent of institutional or hospital care; disease may be progressing rapidly.	40	Disabled; requires special care and assistance.
	30	Severely disabled; hospital admission is indicated although death not imminent.
	20	Very sick; hospital admission necessary; active supportive treatment necessary.
	10	Moribund; fatal processes progressing rapidly.
	0	Dead

**APPENDIX C: Cockcroft-Gault Formula**

$$eC_{Cr} = \frac{(140 - \text{Age}) \times \text{Mass (in kilograms)} \times [0.85 \text{ if Female}]}{72 \times \text{Serum Creatinine (in mg/dL)}}$$

## **APPENDIX D: NCI Common Terminology Criteria for Adverse Events Version 4.0**

Adverse Events will be scored using the NCI Common Terminology Criteria for Adverse Events (CTCAE) Version 4.0.

A copy of the NCI CTCAE Version 4.0 can be downloaded from:

[http://evs.nci.nih.gov/ftp1/CTCAE/CTCAE\\_4.03\\_2010-06-14\\_QuickReference\\_5x7.pdf](http://evs.nci.nih.gov/ftp1/CTCAE/CTCAE_4.03_2010-06-14_QuickReference_5x7.pdf)

## **APPENDIX E: Medwatch 3500**

Reportable adverse events and pregnancies will be reported to the appropriate on a Medwatch 3500 form. The most recent Medwatch 3500 Form can be retrieved from [http://www.fda.gov/medwatch/safety/FDA-3500\\_fillable.pdf](http://www.fda.gov/medwatch/safety/FDA-3500_fillable.pdf)
